9.2.1 Treatment Assignment Procedures

Randomization will be implemented using randomly permuted blocks of size two, stratified on clinic, age (70-79 vs. 80-89), and race/ethnicity (white vs. non-white). This will maximize blinding of outcome assessors and achieve balanced groups that accurately reflect the underlying composition of the study population, as a primary aim of the study is to lay the groundwork for future large, multisite trials in integrated healthcare systems in the US. The randomization sequences will be generated in advance by the study statistician, securely stored electronically, and accessible only to intervention staff.

Research staff who enroll study participants and collect outcome data will be unaware of the randomization sequence and will be blinded to group assignment. Staff will be instructed not to seek information about study group. Outcome assessors will be blinded to group assignments. The content of interviewer scripts will be designed to deliberately reduce the chance of disclosure, using procedures and language that [name] used in an R21 pilot RCT with blinded assessors. Assessors will document if they become unblinded; a different blinded assessor will perform any further follow-up assessments. Data analysts will also be blinded as to group assignment by using codes for randomization groups.

If unblinding occurs, the following will be recorded:

- The ID of the unblinded participant
- The reason for unblinding
- The study staff person responsible for unblinding

- A list of person(s) who have been unblinded
- Future assessments will be performed by team members who remain blinded.

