5.2.3 Screening Evaluation

Approximately one week after letters have been mailed, potentially eligible study participants will be called and study interviewers will describe the study activities, randomization, and risks and benefits of the study. They will confirm understanding and invite any questions. They will obtain verbal informed consent to collect demographic information, to continue with the screening process, and (for those eligible for the study) to wear the ActiGraph activity monitor for a week. Once verbal consent has been given, they will give a detailed description of the study and determine final eligibility with a standardized screening questionnaire.

Because our goal is to enroll people with low normal cognitive function, we will also perform the short telephone version of the CASI. Enrollment will be restricted to those whose scores fall between 25 and 32 inclusive (see inclusion criteria section for rationale). Individuals who are eligible and interested will then be scheduled for in-person written consent and baseline assessment, and will be sent an accelerometer by

mail to obtain a measure of baseline levels of physical activity.

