5.2.4 Baseline and Randomization

Consenting Procedure

At the written consent and baseline measurement visit, the assessor will discuss the nature of the study and review the written consent and HIPAA authorization form. Adequate time will be allowed to ensure comprehension and answering any questions. The assessor will obtain written consent from the participant and will also sign the consent form. A copy of the dually signed consent form will be given to the participant. The original will be stored in a locked filing cabinet in KPWHRI's locked offices. The consent forms will be stored separately from study ID and measures.

Baseline Assessments

All participants will complete the assessments listed below at baseline and three follow-up visits spaced over 24 months (approximately 6, 12, and 24 months), plus the option of a phone assessment or a mailed questionnaire at 18 months. Details of the assessments are below, in section 5.3.

- ActiGraph: objectively measures physical activity (worn for a week before baseline visit)
- Physical Function Tests
 - Short Physical Performance Battery
- Vital Signs
 - Height and weight
 - Blood pressure
- Questionnaire packet
 - Memory and Thinking Questionnaire (Cognitive Function Instrument)
 - Health Questionnaire (PROMIS Global Health)
 - Exercise Questionnaire (Rapid Assessment of Physical Activity in Older Adults: RAPA)
 - Social Activities Questionnaire (PROMIS Satisfaction with Participation in Discretionary Social Activities)
 - Leisure Activities Questionnaire (Cognitive Activities Questionnaire)
 - Alcohol and Smoking Questionnaire (AUDIT-C and Smoking Use)
 - Diet Questionnaire (MIND Diet)
 - Mood Questionnaire (Center for Epidemiological Studies Depression Scale: CES-D)
 - Sleep Questionnaire (Pittsburgh Sleep Quality Index: PSQI)
- Neuropsychological Test Battery
 - Verbal memory (WMS-R Logical Memory)
 - Verbal memory (CERAD Word List)
 - Attention/Working memory (WAIS-R Digit Span)
 - Speed (WAIS-R Digit Symbol)

- Speed/Executive (Trail Making Test)
- Speed/Executive (Stroop Test)
- Language (Category Fluency Test)
- Language/Executive (Phonemic Fluency)
- Cognitive Abilities Screening Instrument (baseline, 6, 12, and 24 months; Telephone CASI at 18 months for phone assessments)

Randomization

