Study participants will be randomized after the baseline visit in a 1:1 ratio to treatment and control, using procedures described below in Section 9.2.1. The study intervention will begin within eight weeks of randomization. If an appointment with the interventionist has not been scheduled within eight weeks of randomization, a case review will take place between the clinical support team and the intervention team to decide the best way to continue with the participant.

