6 STUDY INTERVENTIONS

6.1 Interventions, Administration, and Duration

SMARRT Intervention Arm

After baseline assessments have been completed, the intervention team (including a nurse care manager and a behavioral interventionist) will use a standardized procedure to develop an individualized Alzheimer's Risk Profile for each patient randomized to the SMARRT intervention arm. This will include a graphic display of the targeted risk factors showing areas where the participant is doing well (green), areas where they can continue to improve (orange), and areas that are of particular risk for them (red). Patients will then meet in-person with an interventionist to review their risk profile and develop a personalized risk reduction action plan. Interventionists will elicit participants' values and motivators to reduce Alzheimer's risk and will use a decisional balance process informed by motivational interviewing and confidence ratings to help them choose 1-3 specific, achievable risk reduction steps that they are most ready to adopt. Participants will be provided with tools to track their progress. At each subsequent visit, interventionists will review progress, problem-solve barriers, and set new goals as needed. Targeted areas will include: increasing physical, mental and social activities; quitting smoking; healthy diet; controlling cardiovascular risk factors (diabetes, hypertension); reducing depressive symptoms; improving sleep; and decreasing use of potentially harmful medications. Following detailed protocols, the intervention team will provide counseling if participants experience distress related to being informed of their Alzheimer's risk.

Interventionists will provide participants with a menu of options for each targeted risk factor, and goals will be individualized to preferences, barriers, and motivators up front to optimize intervention adherence (see Table below). For each target, there are options that leverage technology as appropriate for the participants' interest and skill level. Non-technology-based options are provided for each target as well.

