10.2 Data Management

Data will be collected and stored separately for enrollment and intervention activities and outcomes activities (secure, web-based data entry system overseen by UCSF; no PHI). All data will be collected by KPWHRI staff in KPWA facilities. The following is a list of study data management responsibilities which will be undertaken by the clinical site (KPWHRI) to ensure protection of participant privacy:

Electronic files and paper forms – Identifiable data (PHI or PII) will be stored in a separate file from study data, all in a secure location. Computers are password-protected and filing cabinets are kept locked.

Computer security – Computers are password-protected with multiple levels of permissions and systems knowledge required to access study data. Users receive security training, including annual compliance trainings. The system is routinely backed up in an off-site server to prevent loss of data.

Data listings and distribution – No PHI or PII will be included in any published data listing. It will not be distributed without proper institutional agreements and IRB approval in place.

Access and storage – Participant records will not be accessible to persons outside of KPWHR and UCSF without the express written consent of the participant. KPWHR offices are locked at all times to protect computer records and paper files locked in filing cabinets. Guests must be escorted. Precautions will be maintained during and after the study period for as long as the records are retained.

Data disposal – After the appropriate retention period passes, study files will be disposed of in an appropriate manner. Computer files will be deleted. Paper files will be placed in a locked confidential shred bin.

KPWHR (Clinical Site) study staff control the data entry into UCSF's secure web-based data entry site, called REDCap. UCSF (Coordinating Center) controls the return of data via KPWHR's Secure File Transfer site.

The Coordinating Center (UCSF) will receive a limited dataset (outcomes data, including cognitive testing and risk factor data) labeled by study ID; no PHI will be entered. This data will be stored in UCSF's secure web-based data entry system, REDCap. Outcomes data from REDCap will be transmitted back via KPWHR's Secure File Transfer. Additionally, UCSF will receive audio recordings of selected cognitive testing batteries for the study neuropsychologist to monitor. These recordings, although coded, are considered PHI.

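### Section 9.2.1 gives intervention staff access to the pre-generated randomisation sequences, and the plan does not say who assigns, in what order, or how upcoming assignments stay hidden

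*Combined protocol and SAP*

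**What the plan says.** On custody of the list, Section 9.2.1 reads: "The randomization sequences will be generated in advance by the study statistician, securely stored electronically, and accessible only to intervention staff". What is made accessible is the sequence, not the result for one participant. The same section uses permuted blocks of two within strata formed by clinic, age group and race/ethnicity. It then adds a safeguard: "Research staff who enroll study participants and collect outcome data will be unaware of the randomization sequence and will be blinded to group assignment".

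The order of events is clear:

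- Section 5.2.3: interviewers, by telephone, "determine final eligibility with a standardized screening questionnaire".
- Section 5.2.4, consent and baseline visit: "The assessor will obtain written consent from the participant and will also sign the consent form".
- Section 5.2.4, after that visit: "Study participants will be randomized after the baseline visit in a 1:1 ratio to treatment and control".
- Section 6.1: the intervention team's described work begins once baseline is done, with participants assigned to SMARRT.

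Section 10.2 places the outcomes data in a "secure web-based data entry system, REDCap", and keeps enrolment and intervention data separate from outcomes data.

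No section names the person or system that makes the assignment. None sets the order in which waiting participants are taken or the interval between baseline and randomisation. None describes one-at-a-time release, registration that cannot be undone, or a log.

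**The concern.** Concealment has to last until the moment of assignment, and it has to cover whoever makes the assignment as well as whoever recruits. Here the only staff given access to the sequence are those who deliver SMARRT. They aim for at least monthly contact with each SMARRT participant for two years (Section 6.1), so they have an interest in who joins their caseload. If two people in one stratum are waiting, the order of entry decides who gets SMARRT, and someone who knows the next slot could choose that order.

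At stake is comparability of the arms on traits that the analysis does not adjust for. The models in Section 9.4 adjust for the baseline value of each outcome. They do not adjust for clinical complexity or readiness to change, and the baseline battery in Section 5.2.4 contains no readiness measure. Such traits could bear on the risk-factor outcomes in particular. The trial is also meant to supply effect estimates for a larger multisite trial, so a loose allocation procedure could be carried forward.

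**Working it through.** The plan gives no figure to reproduce, because the point is procedural. The check is a reading of the sections together, followed by an illustration of possible size.

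**1. Where the sequence could have influence**

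| Step | Who acts | Knows the sequence? |
|---|---|---|
| Telephone eligibility (5.2.3) | Interviewers | No, as enrolling staff (9.2.1) |
| Consent and baseline (5.2.4) | Assessor | No (9.2.1) |
| Assignment (5.2.4, 9.2.1) | Not stated | Not stated; only intervention staff are given access |
| Intervention (6.1) | Intervention team | Has access |

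Unless the list leaks to recruiters, it cannot affect who is enrolled. The open step is assignment: the order or timing with which people in the same stratum, who have finished baseline, are given slots.

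**2. Predictability**

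In blocks of two, a person who knows only the past assignments in a stratum guesses the first of each block with probability 0.5 and knows the second. The rate of correct guesses is (0.5 + 1)/2 = 0.75. A person who can read the list knows every assignment. Hiding the list therefore helps, but a fixed order of registration is needed as well.

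**3. Possible imbalance in a trait**

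Inputs:

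- 100 participants per arm (Sample Size and Population), so about 100 within-stratum pairs.
- q, the share of pairs in which order is chosen on a trait instead of by arrival. This is an assumption; the documents give neither the number of clinics nor waiting times.
- The trait is standard normal, and staff rank the two people perfectly. Both are assumptions.

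For two independent standard normal values, E|X1 − X2| = 2/√π = 1.128. Pairs taken in order of arrival contribute zero on average, so the expected difference between arms is 1.128 × q.

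**4. From trait to outcome**

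A trait imbalance shifts the outcome only in proportion to r, the trait–outcome association given baseline score. The documents give no r. For illustration, r runs from 0.1 to 0.5:

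| q | Trait imbalance (SD) | Outcome shift, r = 0.1 (SD) | Outcome shift, r = 0.5 (SD) |
|---|---|---|---|
| 0 | 0 | 0 | 0 |
| 5% | 0.06 | 0.01 | 0.03 |
| 10% | 0.11 | 0.01 | 0.06 |
| 20% | 0.23 | 0.02 | 0.11 |

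Section 9.2 states a precision of ±0.08 SD for the primary effect. That figure concerns the cognitive outcome. The trait column is on a different scale and should not be set against it.

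**The case against.** A reader might infer that intervention staff view the whole list, match participants to slots themselves, and can pick who receives SMARRT. The documents do not support that as fact. They do not say who performs the assignment, and access to a stored sequence is compatible with a sequential reveal. That intervention staff assign is a reasonable inference from their being the only group with access, but it is still an inference.

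A reader might also infer that the list can steer recruitment. It cannot, short of a leak: those who screen, consent and assess are unaware of it, and their work is finished before randomisation.

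Four further objections carry weight.

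- **Few opportunities.** Each clinic is split into four age-by-race cells. With 200 participants, two people waiting in the same cell at once may be rare, and q may be zero.
- **Little to select on.** The documents describe no contact between coaches and participants before randomisation. Motivation is explored at a meeting held after assignment to SMARRT (Section 6.1). Complexity visible in the health record could be known, but that is a smaller worry. Stratifying by clinic partly deals with distance.
- **Some detection exists.** The baseline comparisons in Section 9.4 could reveal sorting on measured traits, so it would be wrong to say that the plan could never show it. They would not reveal sorting on unmeasured traits, and no check on order of entry is planned.
- **Timing.** Section 5.2.5 writes of March 2020 in the past tense, so enrolment may be over, although the documents do not say so. A change in wording would then protect no one.

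These limit the size of the concern. They do not remove it, because Section 9.2.1 grants access to the sequence itself, which the intervention team does not need, and no release procedure limits what that access shows.

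**Conclusion.** The point holds as a weakness in a stated rule together with missing procedure. Sequences made in advance are open to the team whose programme is being tested, and the plan leaves unstated who assigns, in what order, and how later assignments are hidden until registration is final. The exposure is confined to reordering or delay among same-stratum participants who are waiting after baseline.

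The imbalance in a trait would be at most about 1.13q SD under perfect ranking within pairs. The effect on an outcome would be smaller by the factor r. Both q and r are unknown, and q may be zero. Nothing in the documents shows that any reordering took place. The change is worth making because the stated method is weaker than an easily available one, not because bias has been shown. Confidence is moderate: the wording on access is explicit, but how it worked in practice is not described.

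**What to change.** Amend Section 9.2.1 to state that:

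1. The sequence is held by the study statistician, or in an access-controlled randomisation function, and intervention staff cannot view it. If REDCap is used, the function must be kept apart from the outcomes forms that blinded assessors use, so that assessor blinding is not put at risk.
2. A named role registers each participant once the baseline visit is recorded as complete, in order of completion.
3. One time-stamped assignment, which cannot be reversed, is then released to intervention staff for that participant only.

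If a sequential reveal was already in use, a sentence describing it and naming who operated it would settle the forward-looking part.

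For participants already randomised, list the baseline-completion date and the assignment order within each clinic, age and race stratum, and report any out-of-order entries. If enrolment has closed, this check is the live action.

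The cost is the set-up of access controls and a short log review. It needs no extra participants or visits.

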9.3 Interim analyses and Stopping Rules

Because this is a pilot study, no interim analyses are planned. The DSMB may request that an interim analysis be performed if there are concerns about participant safety. The interim analysis results will be reviewed in closed session and may be presented in blinded or unblinded format at the DSMB's request. If interim analyses are requested, criteria for stopping the study will be clearly defined in advance by DSMB.

9.4 Data Analyses

We will first assess balance on baseline characteristics of the SMARRT and HE groups using graphical and tabular checks for overlap, and statistical comparisons using t-tests, Wilcoxon, chi-square, and Fisher's exact tests as appropriate. All analyses will use intent-to-treat principles.

Aim 1. To estimate the effect of SMARRT compared to HE on our outcome, repeated measures of the composite cognitive function score obtained at 6, 12, and 24 months, we will use a linear mixed model (LMM), with fixed effects for the baseline score, time, treatment, and the time-by-treatment interaction, as well as random intercepts and slopes. Exploratory analyses will be performed within the intervention group to determine whether there is evidence that the magnitude of the effect varies based on the number or types of risk factors targeted, the extent to which goals are achieved, or the number or type of interventionist contacts. These analyses will be restricted to the intervention group because among controls, the number and type of risk factors targeted will not be assessed, achievement of goals will be undefined, and the number and type of contacts will differ systematically by design. Hence these results will be descriptive and will not estimate effect modification, mediation or dose-response, respectively. We also will use multiple imputation to explore the impact of missing data.

Aim 2. Similar methods will be used to assess the effect of the intervention on continuous Alzheimer's risk factors over two years. Because this is a pilot study, we chose not to pre-specify the benchmarks for change/improvement for each risk factor. Instead, we will quantify the amount of change achieved for each risk factor. Generalized linear mixed models (GLMMs), also with fixed effects for the baseline value, time, treatment, and the time-by-treatment interaction, and random intercepts and slopes, will be used as appropriate to assess treatment effects on binary, count, ordinal, and multinomial risk factors, including the number of risk factors.

Aim 3. LMMs and GLMMs also will be used to compare the impact of SMARRT vs. HE on individual components of the global cognitive score, physical performance, functional ability, quality of life. Finally, Cox proportional hazards models will be used to analyze intervention effects on time to MCI and Alzheimer's.

Based on data from prior Alzheimer's risk reduction trials, differences in intervention effect by gender or by race/ethnicity are not expected. Because the study was not

designed to examine potential differences in intervention effect between gender and racial/ethnic subgroups, the recruitment of women and minorities for the proposed project is expected to reflect the underlying composition of the aged 70+ population enrolled in the KPWHRI health network. As a result, we expect that our study population will not include gender and racial/ethnic subgroups large enough for comparisons of the intervention effect to have high statistical power for detecting clinically meaningful differences.

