Sample Size and Population

200 higher-risk older adults (age 70-89 with low normal performance on cognitive screen

and \geq two modifiable risk factors that will be targeted by our intervention) at baseline will be eligible for randomization. 100 will be randomized to SMARRT, and 100 to HE control. Randomization will be stratified by clinic and blocked by race (white, non-white) and age (70-79, 80-89) to ensure balance in these groups. Study participants will be recruited from selected primary care clinics of Kaiser Permanente Washington (KPWA).

STUDY TEAM ROSTER AND STUDY SITES

Principal Investigators:

[name]

University of California, San Francisco
[name]
[name]
[contact] [name]
[contact]

[name], PhD

Kaiser Permanente Washington
[name]
[name]
[contact]
[contact]

[name], MPH (Former PI)

Kaiser Permanente Washington
[name]
[name]
[contact]
[contact]

Co-Investigators by Site:

University of California, San Francisco

[name]
[name]
PI: [name]

[name], MPH

[name]
[name]
[contact] [name]
[contact]

[name]

[name]
[name]
[name]
[contact]
[contact]

Kaiser Permanente Washington

[name]

[name]

PI: [name], PhD

[name], MPH

[name]

[name]

[contact]

[contact]

[name]

[name]

[name]

[contact]

[contact]

[name]

[name]

[name]

[contact]

[contact]

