1 STUDY OBJECTIVES

1.1 Primary Objective

To collect pilot data on the effect of SMARRT compared to Health Education (HE) control for our primary outcome of two-year cognitive change. We will obtain critical information for estimating sample sizes required for a larger multi-site trial.

Changes made to the protocol due to Covid-19, i.e., switching to telephone data collection, may limit our ability to examine cognitive change effectively, as several of the most important cognitive tests cannot be administered via telephone.

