9.2 Sample Size and Randomization

Because this is a pilot trial, our goal is to estimate effect sizes for a larger trial. Therefore, sample size estimates are based primarily on considerations of precision rather than power and effect size. For our primary outcome, our sample size of 200 will enable us to estimate the effect size with a precision of +/- 0.08 SDs, assuming loss to follow-up of 10%, and ICC of 0.6, based on data from the FINGER trial (4). This estimate will be used in combination with a consensus clinically meaningful effect, based on the literature and investigator expertise. For secondary outcomes, we estimate that precision will range from +/- 0.06 SDs to +/- 0.08 SDs, depending on the ICC. We anticipate that conversion to MCI/AD in this two-year trial will be low (<10%); therefore, this outcome is considered exploratory.

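### The Aim 1–3 models leave out the three factors used to stratify randomisation, so intervals for treatment differences will be slightly too wide if those factors predict outcome beyond the baseline score

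*Combined protocol and SAP*

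**What the plan says.** Section 9.2.1 (Treatment Assignment Procedures) uses "randomly permuted blocks of size two, stratified on clinic, age (70-79 vs. 80-89), and race/ethnicity (white vs. non-white"). The synopsis, under Sample Size and Population, names the same three factors in different words: "Randomization will be stratified by clinic and blocked by race" and age.

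Section 9.4 (Data Analyses) gives the Aim 1 linear mixed model for the 6-, 12- and 24-month composite "with fixed effects for the baseline score, time, treatment, and the time-by-treatment interaction, as well as random intercepts and slopes". The Aim 2 generalized linear mixed models are specified "also with fixed effects for the baseline value, time, treatment, and the time-by-treatment interaction", with the same random effects, and continuous risk factors are handled similarly. Aim 3 uses both model types again, and "Cox proportional hazards models will be used to analyze intervention effects on time to MCI" and Alzheimer's disease.

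No clinic, age-group or race/ethnicity term, and no random effect for clinic, appears in 9.4 or elsewhere. Section 9.4 plans baseline balance checks but ties no adjustment to them.

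**The concern.** Blocks of two keep the arms nearly equal within each clinic-by-age-by-race cell, so most outcome variation between cells cancels from the treatment difference. A model that omits the factors leaves that variation in its random-effect and residual variances and treats it as noise. The reported standard error is then larger than the design warrants. The estimate is still unbiased and the error is conservative.

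This matters here because the pilot's product is an estimate with its uncertainty. Section 9.2 states that "sample size estimates are based primarily on considerations of precision rather than power and effect size", and section 1.1 says "We will obtain critical information for estimating sample sizes required for a larger multi-site trial". An interval wider than the design justifies would carry into that planning.

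**Working it through.** **The plan's own precision figure.** Section 9.2 states ±0.08 SD for N = 200, 10% loss and ICC 0.6. With 90 analysed per arm, unit SD and an assumed 95% level, the half-width is 1.96 × √((2/90) × v):

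- Single follow-up visit adjusted for baseline, v = 1 − 0.6² = 0.64: 0.234.
- Mean of three visits adjusted for baseline, v = (1 + 2 × 0.6)/3 − 0.6² = 0.373: 0.179.
- Slope per visit over four equally spaced visits, v = (1 − 0.6)/5 = 0.08: 0.083. This rounds to the stated figure, but it is not the 0/6/12/24-month schedule and the plan does not name that scale.

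The stated figure is therefore not reproduced for a two-year or visit-averaged difference. The check below uses relative widths, which do not depend on it.

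**Inputs from the documents.** 200 randomised 1:1 in stratified blocks of two; scores at 6, 12 and 24 months; baseline score as covariate; ICC 0.6; 10% loss.

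**Assumed.** Between-person slope SD 0.15 SD/year; 30% aged 80–89; 30% non-white; 5 clinics (3 and 10 also tried); the three factors sharing R² equally. R² is the share of variance in the mean follow-up score, left after baseline, that the factors explain.

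**Closed form without stratum effects.** Residual intercept variance is 0.6 − 0.36 = 0.24, within-person variance 0.4, slope variance 0.15² = 0.0225. Visit times average 1.167 years, with sum of squares 1.167.

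- Average effect: v = 0.4/3 + 0.24 + 1.167² × 0.0225 = 0.404; SE = √(0.404/45) = 0.095.
- Fitted 24-month effect: v = 0.4/3 + 0.833² × 0.4/1.167 + 0.24 + 4 × 0.0225 = 0.701; SE = √(0.701/45) = 0.125.
- Slope: v = 0.4/1.167 + 0.0225 = 0.365; SE = √(0.365/45) = 0.090.

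**Effect of adding the factors.** For the average effect the width ratio is √(1 − R²): 0.975, 0.949 and 0.894 at R² 0.05, 0.10 and 0.20. Level-only stratum variance, 0.404 × R²/(1 − R²), is a smaller share of the 24-month variance. There the ratios are √(0.701/0.723) = 0.985, √(0.701/0.746) = 0.969 and √(0.701/0.802) = 0.935. It does not enter the slope.

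Simulation (4,000 trials per row, 5 clinics) adds the cost of estimating the terms. Percentages were taken before rounding.

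| R² | Average: SE without → with | CI width | 24-month: SE without → with | CI width |
|---|---|---|---|---|
| 0 | 0.0950 → 0.0953 | +0.3% | 0.1251 → 0.1254 | +0.3% |
| 0.05 | 0.0975 → 0.0953 | −2.2% | 0.1270 → 0.1255 | −1.2% |
| 0.10 | 0.1002 → 0.0953 | −4.8% | 0.1292 → 0.1256 | −2.7% |
| 0.20 | 0.1060 → 0.0951 | −10.3% | 0.1336 → 0.1252 | −6.3% |

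- Slope SE is 0.090 with or without the main effects. If those aged 80–89 decline 0.1, 0.2 or 0.3 SD/year faster, an age-group-by-time term narrows the slope interval by 0.2, 1.1 or 2.5%.
- With 3 to 10 clinics, the average-effect interval narrows by 5.0 to 4.4% at R² 0.10 and widens by 0.1 to 0.7% at R² 0.
- Coverage of the unadjusted 95% interval for the average effect is 95.6, 95.7 and 96.3% at R² 0.05, 0.10 and 0.20 (Monte Carlo SE about 0.34 points).
- The true sampling SD of the average effect falls by only 0.6, 1.1 and 2.3%, because the design already supplies most of the balance.

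A second simulation with 4 or 10 clinics defined R² on the 24-month contrast itself. It gave width ratios of 0.976, 0.950 and 0.895 (4 clinics) and 0.981, 0.954 and 0.899 (10 clinics). At R² 0.20, unadjusted coverage was 97.0 and 96.7%. Adjusted coverage stayed between 94.5 and 95.4% throughout.

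**Cox model.** Section 9.2 expects "conversion to MCI/AD in this two-year trial will be low (<10%); therefore, this outcome is considered exploratory". Below 10% of 200 is fewer than 20 events. Treatment plus all factors with 5 clinics is 1 + 4 + 1 + 1 = 7 parameters, or under 3 events each.

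**The case against.** The strongest reply is that this is an efficiency preference. The estimate is unbiased, the test is conservative, and the scheme's stated purposes (assessor blinding and balanced groups) are met whatever the model. That stands, and it limits the point to a minor one.

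The primary outcome is two-year change, so the average over follow-up is not the obvious contrast. The 24-month figures are roughly half as large and the slope does not move. This also stands; section 9.4 does not say which contrast will be reported.

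The upper R² values are demanding. Suppose the factors explain a share p of total single-visit variance, equally at baseline and follow-up. Then R² = 1 − [(1 + 2 × 0.6)/3 − p − (0.6 − p)²/(1 − p)]/0.373. Values of p = 0.10, 0.19 and 0.32 give R² of about 0.05, 0.10 and 0.20. The range 0 to 0.05 is the easiest to defend, and there the 24-month interval changes by +0.3 to −1.2%.

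Nor is the narrowing the same as the excess width. The unadjusted SE exceeds its empirical SD by 0.1002/0.0974 − 1 = 2.9% at R² 0.10 and 0.1060/0.1001 − 1 = 5.9% at 0.20, with about 1.1% Monte Carlo error on each SD. The rest of the narrowing is a small efficiency gain plus that noise.

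The figures are for linear models. With a logit-type link, adjustment also shifts the conditional effect, so a narrower interval cannot be assumed. In addition, section 5.2.5 says key tests were not collected after March 2020, so 180 analysed may be optimistic. Both points bear on how the terms are added. Neither changes the omission, the direction of the error in the linear models, or the low cost of the change.

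**Conclusion.** The point holds. Randomisation is stratified on three factors that the Aim 1 and Aim 2 model specifications omit and that nothing else in the documents restores. In the linear models, intervals for a treatment difference are conservative to the extent that the factors predict outcome beyond baseline. Adding them would narrow the interval by about 1 to 3% at 24 months and 2 to 5% for the average effect at R² of 0.05 to 0.10. At R² of 0.20, the high end, the figures are about 6% and 10%.

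The omission is certain. The size rests on assumed R², clinic number, slope SD and age and race mix. No size is claimed for the generalized linear mixed models. The change is worth making because it aligns the analysis with the design at almost no cost, not because the current analysis is invalid.

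**What to change.** In section 9.4, add fixed main effects for clinic, age group (70–79, 80–89) and race/ethnicity (white, non-white) to the Aim 1 linear mixed model and to the linear and generalized linear mixed models of Aims 2 and 3. Add an age-group-by-time term if faster decline at older ages is to be captured, since main effects do nothing for the slope. For sparse binary outcomes and the Cox model, pre-specify a reduced set, for example clinic as a random effect or stratum term, or clinic omitted.

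The cost is one or two sentences. The variables are already recorded for randomisation. With 5 clinics the terms use 4 + 1 + 1 = 6 degrees of freedom from about 180 participants. If they explain nothing, the interval widens by 0.1 to 0.7% across 3 to 10 clinics.
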